3.5 Drug Interactions

3.5.1 Metabolism, CYP2C8:

Co-administration of a strong CYP2C8 inhibitor (gemfibrozil) increased the composite area under the plasma concentration-time curve (AUC) of enzalutamide plus N-desmethyl enzalutamide by 2.2-fold in healthy volunteers. In current study, co-administration of enzalutamide with strong CYP2C8 inhibitors will be avoided if possible and, if unavoidable, dose reductions will be made according to the manufacture guidelines and SCCA pharmacy assistance.

The effects of CYP2C8 inducers on the pharmacokinetics of enzalutamide have not been evaluated in vivo. Co-administration of enzalutamide with strong or moderate CYP2C8 inducers (e.g., rifampin) may alter the plasma exposure of enzalutamide and will be avoided in this trial if possible.

3.5.2 Metabolism, CYP34A:

Co-administration of a strong CYP3A4 inhibitor (itraconazole) increased the composite AUC of enzalutamide plus N-desmethyl enzalutamide by 1.3-fold in healthy volunteers. Co-administration of enzalutamide with strong CYP3A4 inducers (e.g., carbamazepine, phenobarbital, phenytoin, rifabutin, rifampin, rifapentine) may decrease the plasma exposure of enzalutamide and will be avoided if possible. The effects of CYP3A4 inducers on the pharmacokinetics of enzalutamide have not been evaluated in vivo. Selection of an alternative medication with no or minimal CYP3A4 induction potential is recommended by the manufacturer and this strategy will be utilized whenever possible.

Enzalutamide is a strong CYP3A4 inducer and a moderate CYP2C9 and CYP2C19 inducer in humans. Co-administration with drugs that are metabolized by CYP3A4 (e.g., alfentanil, cyclosporine, dihydroergotamine, ergotamine, fentanyl, pimozide, quinidine, sirolimus and tacrolimus), CYP2C9 (e.g., warfarin) and CYP2C19 (e.g., Semephenytoin) will be avoided when possible and closely monitored when concurrent use is unavoidable.

3.6 Supplier

Enzalutamide used under this study will be provided by from Astellas/Medivation, Inc. and distributed by NCCN's vendor CRMG.

3.7 Drug Accountability

The investigator, or a responsible party designated by the investigator, must maintain a careful record of the receipt, disposition, and return of all drugs received for this study using the study specific Investigational Agent Accountability form.

3.7.1 Return of unused enzalutamide

Patients will be instructed to return unused enzalutamide. All unused drug will be destroyed per institutional Investigational Drug Services policy.

4.0 STAGING CRITERIA

When applicable, the Lugano staging criteria [18] (see Appendix A) will be used; staging should be the highest stage established, either at diagnosis or relapse of disease.

For patients from whom data are available, the mantle cell lymphoma international prognostic index (MIPI) [19] will be documented at the time of diagnosis and enrollment (see Appendix B).

- 5.1.10 Women of childbearing potential must have a negative serum (beta-human chorionic gonadotropin [β-hCG]) or urine pregnancy test at screening. Women who are pregnant or breastfeeding are ineligible for this study.

5.2 Exclusion Criteria

- 5.2.1 Uncontrolled illness including, but not limited to ongoing or active infection, symptomatic congestive heart failure, unstable angina pectoris, cardiac arrhythmia, or psychiatric illness/social situations that would limit compliance with study requirements within 6 months of enrollment.
- 5.2.2 Known active central nervous system lymphoma.
- 5.2.3 Known clinically significant heart disease as evidenced by:
 - Myocardial infarction within 6 months of enrollment.
 - Uncontrolled angina within 6 months of enrollment.
 - Congestive heart failure NYHA Class III or IV, or a history of congestive heart failure NYHA Class III or IV in the past, unless a screening ECHO or MUGA within 3 months results in a left ventricular ejection fraction ≥45%.
 - Clinically significant ventricular arrhythmias.
 - History of Mobitz II second degree or third degree heart block without a permanent pacemaker in place.
 - Bradycardia as indicated by a heart rate < 50 beats per minute at screening visit.
 - Hypotension as indicated by SBP \leq 85 on 2 consecutive measurements at screening visit.

- Uncontrolled hypertension as indicated by SBP > 170 mmHg or DBP
 > 105 mmHg on 2 consecutive measurements at screening visit.
- 5.2.3 Child Pugh class C hepatic dysfunction.
- 5.2.4 History of seizures.
- 5.2.5 Any life-threatening illness, medical condition, or organ system dysfunction which, in the investigator's opinion, could compromise the subject's safety, interfere with the absorption or metabolism of enzalutamide, or put the study outcomes at undue risk.
- 5.2.6 Patients with other prior malignancies except for adequately treated basal cell carcinoma, squamous cell carcinoma of the skin, breast or cervical cancer *in situ*, or other cancer from which the patient has been disease-free for 5 years or greater, unless approved by the protocol Investigator / Lead-Sub-Investigator.
- 5.2.7 Chemotherapy, immunotherapy, biologically targeted therapy, other investigational agent, or radiation therapy within 3 weeks of initiation of enzalutamide therapy. For patients with objectively progressive disease on a BTK-targeting agent whom in the opinion of the investigator would not tolerate a 21 day washout period, a >5 half-lives washout period will be allowed.
- 5.2.8 Prior allogeneic transplant with GVHD requiring ongoing immunosuppressive therapy.
- 5.2.9 HIV-positive individuals on combination antiretroviral therapy are ineligible because of the potential for pharmacokinetic interactions with enzalutamide.
- 5.2.10 Ongoing treatment with hormonal agents (e.g. finasteride, dutasteride, ketoconazole, hormonal birth control, estrogen replacement therapy, testosterone replacement therapy) or herbal products that may have hormonal activity (saw palmetto, black cohosh). Patients taking these agents are eligible for screening, but must be willing to undergo a washout period of 4 weeks prior to starting study treatment.

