9.0 STUDY CALENDAR

- The first three treatment cycles will be 4 weeks (28 days). All subsequent cycles starting with Cycle 4 will be 12 weeks (84 days). Patients may be seen for additional optional mid cycle visits at the discretion of their provider.
- Study drug will be dispensed in a four week supply for the first three cycles, then in a 12 week supply for subsequent cycles

Required Studies	Screening (within 4 weeks of initiation of treatment)	During treatment	Post Therapy	Follow-up ¹⁰
Physical	,			
Medical History	X			
Physical Exam	X	X^7	X ⁹	
Performance Status	X	X^7	X ⁹	
Clinical Disease Assessment	X	X^7	X ⁹	
Adverse Event Assessment	X	X^7	X^9	
EKG	X			
Lab				
CBC and differential	X	X^7	X^9	
Serum creatinine, total bilirubin, SGOT (AST), SGPT (ALT), electrolytes, calcium, glucose	X	X ⁷	X ⁹	
Albumin, LDH, B2M	X		X ⁹	
Bone marrow studies	X^1	X^1		
Pregnancy test	X^2			
Tissue collection, if feasible	X^{11}			
PSA (prostate specific antigen)	X^3	X^3		
Total testosterone and estradiol	X^4	X^4		
Research Labs ⁵	X^5	X ⁵	X ⁹	
Radiology				
CT Chest, abdomen and pelvis (+ neck if clinical involvement)	X	X ⁸		

FDG-PET (skull base to proximal	X^6	X ⁸	
femur)			

- ¹ Bone marrow studies include aspirate and unilateral or bilateral biopsy for standard analysis with additional correlative studies as specified in Section 14. Bone marrow studies should be performed at screening unless approved by the Investigator or Lead Sub-Investigator. If all bone marrow studies are negative at screening, these do not need to be repeated except in the case of progressive disease by CT imaging, if feasible. If bone marrow status is unknown or positive at screening, patients will need to a have bone marrow study to confirm a suspected CR.
- ² Pregnancy test is only required in women of childbearing potential. Pregnancy test will be repeated on the first day of study drug therapy if > 1 week has lapsed from initial screening pregnancy test and start of treatment.
- ³ PSA is only required in men. To be drawn at screening, after 4 weeks of treatment (+/- 6 days), and at treatment discontinuation (+/- 6 days).
- ⁴ Total testosterone and estradiol to be drawn at screening, after 4 weeks of treatment (+/- 6 days), and at treatment discontinuation (+/- 6 days).

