- ⁵Research Labs include blood samples for serum hormone levels (DHT, DHEA, Androstenedione, Estrone). To be drawn at screening, after 4 weeks of treatment (+/- 6 days), after 12 weeks of treatment (+/- 6 days), and then every 12 weeks (+/- 6 days) during treatment. ⁶ May be obtained up to 8 weeks in advance of initiation of therapy (provided no additional anti-cancer therapies are administered during the interval). A Deauville score should be assigned.
- ⁷ At the beginning of therapy (within 3 days), then every four weeks for the first 12 weeks (+/- 6 days), then at a minimum of every 12 weeks (+/- 6 days) while on therapy, depending on clinical course. For the first day of therapy, pre-entry H&P, PS, disease assessment, and adverse event assessment may be used (these do not need to be repeated within 3 days) and labs done within 14 days are acceptable.
- ⁸ During treatment, restaging CT imaging will be performed every 12 weeks of therapy (+/- 7 days), or as indicated to evaluate clinical suspicion of disease progression. First restaging CT (three months after initiating therapy) should include PET imaging to ascertain metabolic response to therapy. Subsequently, restaging PET/CT should also be performed to confirm metabolic CR in patients with stable PR on 2 consecutive CT staging exams or in patients with a CR based on CT staging and baseline FDG-avid disease to determine metabolic CR and CR (resp.). A Deauville score should be assigned when restaging PET is performed.
- ⁹ Post therapy evaluation will be completed 30 days (+/-7 days) after the last dose of enzalutamide or prior to initiation of new therapy, whichever comes sooner.
- ¹⁰Long-term follow-up should be performed according to the patient's physician's standard of care. This may be performed at patients' local physician's offices. Long-term follow-up will assess survival and disease progression; subjects may be contacted by the study team until five years out from study completion, subject withdrawal of consent, lost to follow-up, or study termination by the investigator, whichever occurs first.
- ¹¹ When appropriate, archival tissue or fresh samples from clinical biopsies may be used.

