14.0 CORRELATIVE STUDIES

14.1 Objectives

- 14.1.1 To determine whether pre-treatment expression of AR and ER in tumor, or levels of androgens and estrogens in serum associate with response to therapy in MCL patients treated with enzalutamide.
- 14.1.2 To determine whether lack of AR expression or presence of truncated AR splice variants associate with poor response to therapy in MCL patients treated with enzalutamide

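### The only baseline PSA and hormone sample need not follow the hormonal-agent washout, so for washout patients it may not describe the hormonal state at first dose

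*Combined protocol and SAP*

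**What the plan says.** Section 5.2.10 of the protocol excludes "Ongoing treatment with hormonal agents (e.g. finasteride, dutasteride, ketoconazole, hormonal birth control, estrogen replacement therapy, testosterone replacement therapy") and herbal products that may act hormonally. It then opens a route in: anyone on such an agent is "eligible for screening, but must be willing to undergo a washout period of 4 weeks prior to starting study treatment".

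The Section 9.0 calendar heads the pre-treatment column "Screening (within 4 weeks of initiation of treatment"). Three footnotes fix the sampling times:

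- Footnote 3: "PSA is only required in men. To be drawn at screening, after 4 weeks of treatment (+/- 6 days"), and at discontinuation.
- Footnote 4: "Total testosterone and estradiol to be drawn at screening, after 4 weeks of treatment (+/- 6 days"), and at discontinuation.
- Footnote 5, for DHT, DHEA, androstenedione and estrone: "To be drawn at screening, after 4 weeks of treatment (+/- 6 days), after 12 weeks of treatment (+/- 6 days"), then every 12 weeks on treatment.

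Footnote 7 defines a start-of-therapy visit. In the calendar it is attached to the examination, performance status, disease and adverse-event assessments, blood count and chemistry, but not to PSA or the hormones.

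Correlative objective 14.1.1 covers pre-treatment AR and ER expression in tumor, or "levels of androgens and estrogens in serum associate with response to therapy in MCL patients treated with enzalutamide". Section 14.2.1 takes the timing of the serum hormone measurements from the calendar. Neither section says how washout patients are handled.

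**The concern.** The screening window and the washout are both four weeks long, and both end at the first dose. A patient who stops a hormonal agent at the start of screening is in washout for the whole period in which the single baseline sample may be taken. Several of the listed agents are themselves androgens or estrogens, the classes of hormone that objective 14.1.1 measures.

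Two things are at stake. First, the value entered for objective 14.1.1 may not describe the patient's hormonal state when enzalutamide starts. Second, the next scheduled sample is at week 4 of treatment. Anyone who compares it with the screening value could be reading two changes at once: withdrawal of the earlier agent and the effect of enzalutamide. A sample not taken before the first dose cannot be obtained later.

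**Working it through.** The point concerns timing and rests on no sample-size or power figure. The plan states no figure of its own to reproduce.

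**Inputs**

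- W = days from the last dose of the hormonal agent to the first dose of enzalutamide. Section 5.2.10 requires 4 weeks, so W is at least 28 if the requirement is read as a minimum.
- d = days from the baseline draw to the first dose. The calendar allows d from 0 to 28.

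**Formula**

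Washout days completed at the draw = W - d. The washout is complete at the draw only if d is no more than W - 28.

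**Results (washout days completed at the draw)**

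| Draw on day | W = 28 | W = 35 | W = 42 | W = 56 |
|---|---|---|---|---|
| -28 | 0 | 7 | 14 | 28 |
| -21 | 7 | 14 | 21 | 35 |
| -14 | 14 | 21 | 28 | 42 |
| -7 | 21 | 28 | 35 | 49 |
| -1 | 27 | 34 | 41 | 55 |
| 0 | 28 | 35 | 42 | 56 |

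The permitted window has 29 days, from day -28 to day 0. The number of those days on which a draw would follow at least 28 days of washout is:

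- W = 28: 1 of 29 (3%)
- W = 35: 8 of 29 (28%)
- W = 42: 15 of 29 (52%)
- W = 56: 29 of 29 (100%)

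These are counts of permitted days. They are not probabilities, because the documents do not say when in the window blood is usually drawn.

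**Footnote 7**

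For the first day of therapy, footnote 7 accepts laboratory tests up to 14 days old. If the baseline draw were simply attached to that visit, a patient with W = 28 could still be sampled after 28 - 14 = 14 washout days. The allowance therefore has to be switched off explicitly.

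**A comparable rule in the same calendar**

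Footnote 2 has the pregnancy test repeated on the first day of treatment if more than a week has passed since the screening test. The hormone and PSA footnotes have no such rule.

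**Number of patients**

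The documents do not say how many patients will enter through the washout route, and it could be none. Assuming 1 to 4 of the planned 20, the share is 1/20 = 5% to 4/20 = 20%.

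**The case against.** The strongest reply is that the plan permits a sound baseline: a draw on day 0 complies, and so does a longer washout with a later draw. That stands. A reader might infer that the baseline is invalid for every patient who enters through 5.2.10. The documents do not support this, since 5.2.10 does not say when the washout begins and the calendar does not say when in screening blood is drawn.

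A second reply is that a value taken partway through washout may already be close to the patient's own level. That depends on how quickly each agent clears, which the documents do not give. For the same reason they support no conclusion on whether four weeks is long enough, or on the direction in which DHT or PSA would move after an agent is stopped.

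Third, Section 14 is thinner than a reader might assume. In 14.1.1 the word for pre-treatment sits directly on the tumor expression clause, and its extension to serum levels is a natural reading but not an explicit one. Section 14.2.1 speaks of serial measurement. PSA appears in no Section 14 objective or method, and no analysis of change from screening to week 4 is specified. So the week-4 point applies only if such a comparison is made. The screening sample is still the only pre-treatment hormone value available for 14.1.1.

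Finally, the objective is exploratory, and the eligibility records should allow washout patients to be flagged or left out. Flagging would limit the damage, but it would not supply the missing value.

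**Conclusion.** The concern holds as a gap in the sampling rule: the baseline PSA and hormone sample is not required to follow the 5.2.10 washout. For a patient with the minimum 28-day washout, any draw before day 0 falls 1 to 28 days short of a complete washout. The value used for objective 14.1.1 may therefore reflect the withdrawn agent or an incomplete washout.

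The reach is limited. Only patients who wash out a hormonal agent are affected, and their number is unknown. How far any one value is distorted cannot be derived from the documents. The primary endpoint, best overall response rate, is unaffected.

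The conclusion assumes that four weeks is a minimum, that 14.1.1 uses the screening value as its serum baseline, and that the part of Section 7 before 7.2, which was not in the text available for this check, contains no contrary sampling rule. The change is worth making because it costs little and a missed sample cannot be recovered.

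**What to change.** In footnotes 3, 4 and 5 of the calendar, state that for patients who undergo a 5.2.10 washout the baseline PSA and hormone sample is drawn after the washout is complete and before the first dose. State also that footnote 7's 14-day laboratory allowance does not apply to this sample. In Section 14, name it as the baseline for objective 14.1.1 and for any comparison with later values, and flag these patients in the correlative analysis.

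The cost is three footnote edits, a sentence in Section 14 and possibly one extra blood draw at the start-of-therapy visit for washout patients. Results would not be available at registration, but no criterion in Section 5 uses them. The washout length and the dosing are untouched.

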6.0 REGISTRATION

Patients must be registered prior to the start of protocol therapy. A completed eligibility checklist with source documentation, a copy of the signed consent form, and a signed HIPAA authorization are required for registration. All of the eligibility requirements according to Section 5 must have been met.

7.2 Administration of Enzalutamide

Enzalutamide is taken orally at a starting dose of 160 mg daily. Enzalutamide can be taken with or without food. Enzalutamide may be taken at any time during the day, but should be taken at the same time each day. A missed dose should be taken as soon it is remembered. If twelve or more hours have lapsed since a missed dose, participants should not take the missed dose; rather the participant should resume dosing at the next scheduled dose.

Drug	Dose	Route	Days	Duration
Enzalutamide	Starting dose of 160 mg, as four 40 mg	PO	Once daily	Until disease
	capsules. Can be taken with or without			progression, intolerance,
	food. Capsules should be swallowed			or decision of patient or
	whole with water. Do not chew,			treating physician
	dissolve, or open capsules.			

7.3 Prophylaxis

No prophylactic therapy is required for enzalutamide. Supportive care should be provided as clinically indicated.

7.4 Criteria for removal from protocol treatment:

- Documented progression of disease (see section 10.4).
- Development of seizures, or any therapy-related non-hematologic grade ≥ 4 toxicity or other serious adverse event as defined in section 12.0 will qualify for consideration of removal from protocol treatment.
- Development of any other unacceptable toxicity.
- Delay of treatment for more than 21 days due to toxicity.
- The patient may withdraw from the treatment at any time for any reason.
- Taking prohibited medications concurrent with enzalutamide therapy may result in removal from protocol treatment.

8.0 DOSAGE MODIFICATIONS

8.1 Toxicity Management, Dose Modification and Dose Delay

If a patient experiences a \geq Grade 3 non-hematological toxicity related to the study drug or an intolerable side effect, treatment will be withheld for one week or until symptoms improve to \leq Grade 2 or baseline, at which point treatment will

be resumed at the same dose or at a reduced dose (120 mg or 80 mg), based on clinician judgment.

8.2 Concomitant Therapy

Medications used during the course of the study should be documented.

8.2.1 Prohibited Concomitant Therapy:

The administration of concurrent medications intended to treat the primary cancer is not allowed during protocol therapy. This includes any chemotherapy, investigational agent, biologic agent or other anti-tumor agents.

The administration of concomitant medications with effects on drug metabolizing enzymes known to be involved in the metabolism of enzalutamide should be avoided where possible, as detailed in section 3.5 and summarized in the table below.

Class	Example Drugs	Recommendation
Strong CYP2C8 Inhibitors	Gemfibrozil	If co-administration with gemfibrozil cannot be avoid, reduce enzalutamide dose
Strong CYP2C8 Inducers	Rifampin	Avoid concomitant use
Strong CYP3A4 Inhibitors	Itraconazole	No initial dose adjustment
Strong/Moderate CYP3A4 Inducers	Carbamazepine, phenobarbital, phenytoin, rifabutin, rifamin, rifapentine, osentan, efavirenz, etravirine, modafinil, nafcillin, St. John's Wort	Avoid concomitant use
CYP3A4 Substrate	Alfentanil, cyclosporine, dihydroergotamine, ergotamine, fentanyl, pimozide, quinidine, sirolimus and tacrolimus	Avoid concomitant use of substrates with a narrow therapeutic index
CYP2C9 Substrate	Phenytoin, warfarin	Avoid concomitant use of substrates with a narrow therapeutic index
CYP2C19 Substrate	S-mephenytoin	Avoid concomitant use of substrates with a narrow therapeutic index
CYP2C8 Substrate	Pioglitazone	No dose adjustment

Patients should be strongly discouraged from taking any "alternative" or "naturopathic" medications since these agents may interact with study treatment. Concomitant use of these medications should be documented and evaluated by the treating investigator.

Hematopoietic growth factors and transfusions are allowed.

Localized radiation therapy will be allowed for symptom control as needed.

9.0 STUDY CALENDAR

- The first three treatment cycles will be 4 weeks (28 days). All subsequent cycles starting with Cycle 4 will be 12 weeks (84 days). Patients may be seen for additional optional mid cycle visits at the discretion of their provider.
- Study drug will be dispensed in a four week supply for the first three cycles, then in a 12 week supply for subsequent cycles

Required Studies	Screening (within 4 weeks of initiation of treatment)	During treatment	Post Therapy	Follow-up ¹⁰
Physical	,			
Medical History	X			
Physical Exam	X	X^7	X ⁹	
Performance Status	X	X^7	X ⁹	
Clinical Disease Assessment	X	X^7	X ⁹	
Adverse Event Assessment	X	X^7	X^9	
EKG	X			
Lab				
CBC and differential	X	X^7	X^9	
Serum creatinine, total bilirubin, SGOT (AST), SGPT (ALT), electrolytes, calcium, glucose	X	X ⁷	X ⁹	
Albumin, LDH, B2M	X		X ⁹	
Bone marrow studies	X^1	X^1		
Pregnancy test	X^2			
Tissue collection, if feasible	X^{11}			
PSA (prostate specific antigen)	X^3	X^3		
Total testosterone and estradiol	X^4	X^4		
Research Labs ⁵	X^5	X ⁵	X ⁹	
Radiology				
CT Chest, abdomen and pelvis (+ neck if clinical involvement)	X	X ⁸		

FDG-PET (skull base to proximal	X^6	X ⁸	
femur)			

- ¹ Bone marrow studies include aspirate and unilateral or bilateral biopsy for standard analysis with additional correlative studies as specified in Section 14. Bone marrow studies should be performed at screening unless approved by the Investigator or Lead Sub-Investigator. If all bone marrow studies are negative at screening, these do not need to be repeated except in the case of progressive disease by CT imaging, if feasible. If bone marrow status is unknown or positive at screening, patients will need to a have bone marrow study to confirm a suspected CR.
- ² Pregnancy test is only required in women of childbearing potential. Pregnancy test will be repeated on the first day of study drug therapy if > 1 week has lapsed from initial screening pregnancy test and start of treatment.
- ³ PSA is only required in men. To be drawn at screening, after 4 weeks of treatment (+/- 6 days), and at treatment discontinuation (+/- 6 days).
- ⁴ Total testosterone and estradiol to be drawn at screening, after 4 weeks of treatment (+/- 6 days), and at treatment discontinuation (+/- 6 days).
- ⁵Research Labs include blood samples for serum hormone levels (DHT, DHEA, Androstenedione, Estrone). To be drawn at screening, after 4 weeks of treatment (+/- 6 days), after 12 weeks of treatment (+/- 6 days), and then every 12 weeks (+/- 6 days) during treatment. ⁶ May be obtained up to 8 weeks in advance of initiation of therapy (provided no additional anti-cancer therapies are administered during the interval). A Deauville score should be assigned.
- ⁷ At the beginning of therapy (within 3 days), then every four weeks for the first 12 weeks (+/- 6 days), then at a minimum of every 12 weeks (+/- 6 days) while on therapy, depending on clinical course. For the first day of therapy, pre-entry H&P, PS, disease assessment, and adverse event assessment may be used (these do not need to be repeated within 3 days) and labs done within 14 days are acceptable.
- ⁸ During treatment, restaging CT imaging will be performed every 12 weeks of therapy (+/- 7 days), or as indicated to evaluate clinical suspicion of disease progression. First restaging CT (three months after initiating therapy) should include PET imaging to ascertain metabolic response to therapy. Subsequently, restaging PET/CT should also be performed to confirm metabolic CR in patients with stable PR on 2 consecutive CT staging exams or in patients with a CR based on CT staging and baseline FDG-avid disease to determine metabolic CR and CR (resp.). A Deauville score should be assigned when restaging PET is performed.
- ⁹ Post therapy evaluation will be completed 30 days (+/-7 days) after the last dose of enzalutamide or prior to initiation of new therapy, whichever comes sooner.
- ¹⁰Long-term follow-up should be performed according to the patient's physician's standard of care. This may be performed at patients' local physician's offices. Long-term follow-up will assess survival and disease progression; subjects may be contacted by the study team until five years out from study completion, subject withdrawal of consent, lost to follow-up, or study termination by the investigator, whichever occurs first.
- ¹¹ When appropriate, archival tissue or fresh samples from clinical biopsies may be used.

